2.5.4. Safety Endpoints

- Incidence of adverse events (AEs): by System Organ Class (SOC) and Preferred Term (PT) (Medical Dictionary for Regulatory Activities (MedDRA) coded term), by maximum severity, related to study drug, leading to study drug discontinuation, serious, leading to death, and adjudicated.
- Incidence of AEs of clinical interest: HF hospitalisation and CV death.
- Incidence of Special Situation Events.
- Incidence of event adjudication (Hospitalisation, Urgent HF visit and Deaths).
- Incidence of related AEs of special interest: Hypersensitivity reactions, Hypophosphatemia, Injection/infusion site reactions and Haemosiderosis.
- Clinical laboratory panels (absolute and change from baseline, incidence of laboratory abnormalities).
- Vital Signs (absolute and change from baseline).
- Electrocardiograms (incidence of electrocardiogram abnormalities, QTc measurement meeting ICH E14 criteria [2]).
- Prior, concomitant and newly started medications.

Note: biomarkers exploratory analyses will not be part of the CSR of the main study. They will be described in a separate biomarker SAP.

3. ANALYSIS POPULATIONS

3.1. Population Definitions

The following subject populations will be evaluated and used for presentation and analysis of the data:

Screened population

The screened population will consist of all subjects who signed an informed consent form.

All Randomised

The All Randomised set will consist of all subjects randomised to either of the two treatment groups. The All Randomised set will be analysed based on the randomised treatment arm.

Full Analysis Set

The Full Analysis Set (FAS) will consist of all subjects who satisfy the following criteria:

- Randomised to either of the two treatment groups, and
- The administration of study drug was started.
- At least one post-baseline visit (including calls), death or hospitalisation or subjects without post-baseline assessment who withdrew from the study after but not on the randomisation date.

Additionally, subjects with protocol deviation concerning inclusion criteria no. 5 (*Subject (or legally acceptable representative) has provided the appropriate written informed consent. Subject must provide written informed consent before any study-specific procedures are performed.*) will be excluded from FAS.

Subjects in the FAS will be analysed based on their randomised treatment arm.

Per-Protocol Set

The Per-Protocol (PP) analysis set will consist of all subjects in the FAS who had no major protocol violations (see Appendix I).

Safety Set

The Safety (SAF) analysis set will consist of all randomised subjects for whom the administration of study drug has started. Subjects will be analysed according to the treatment received.

The analysis sets to be used for analyses are described in the table below.

Table 2 Analysis Sets

Analyses	Screened population	All Randomised	FAS	PP	SAF
Subject disposition	✓	✓			
Protocol deviations/violations		✓			
Demographics			✓	✓	✓
Baseline characteristics (prior, concomitant and newly started medications, medical history including surgical history and procedures)			✓	✓	✓
Prior medications, concomitant, newly started medications			✓		✓
Medical History and history of cardiovascular factors.			✓	✓	✓
Compliance and exposure					✓
Primary endpoint			✓	✓	
Secondary endpoints			✓	✓	
Other endpoints			✓	✓	
KCCQ-12			✓	✓	
EQ-5D			✓	✓	
AEs, SAEs, and special situations					✓
Event Adjudications					✓
Laboratory parameters					✓
ECGs					✓
Vital Signs					✓

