6.2 Blinding

This is a double-blind trial with randomisation concealment and neither the Investigator, the subject nor Sponsor (or representative) will be aware of the administered study treatment to each subject. The Vifor Pharma Safety Department will have access to the randomisation codes as will investigational sites should the need to unblind a subject arise.

As the FCM and placebo solutions differ in appearance and the study treatment boxes will not be blinded, unblinded study personnel not involved in any study assessments (other than assessment and interpretation of post-randomisation laboratory test results) will be responsible for handling the study treatment boxes, and preparing and administering the study treatment injections in black syringes and using a curtain (or similar) to maintain subject blinding. Unblinded personnel will make sure the subject is not able to observe the preparation of study treatment injections.

Post-baseline iron values should be seen only by the unblinded study physician, who will then be responsible for evaluating the parameters. This physician must review the parameters to confirm the subject well-being and follow guidance per Section [10.2.6](#).

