12.3 Analysis Sets

12.3.1 Full Analysis Set

The full analysis set (FAS) will consist of all subjects who satisfy the following criteria:

- Randomised to either of the two treatment groups
- The administration of study treatment was started

The FAS data set will be analysed based on the randomised treatment arm.

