4.2.14. Time on Study

Time on study for safety purposes is calculated for each subject from SD1 to the last known date:

$$\text{Time on study (days)} = (\text{Last Known Date} - \text{SD1}) + 1.$$

Time on study for efficacy purposes is calculated for each subject from randomisation date to the last known date:

$$\text{Time on study (days)} = (\text{Last Known Date} - \text{Randomisation Date}) + 1.$$

If last known date is outside of visit window for Week 52 visit (i.e. after study day 375), time on study will be 375 days for such subjects and only events up to this day will be considered.

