4.6. Efficacy Evaluation

The analysis of the primary, secondary and other outcomes described below will be performed on the FAS. Sensitivity analyses will be performed on the PP analysis set.

Due to the Covid-19 pandemic, a sensitivity analyses will be performed for the primary and secondary endpoints on the FAS censoring subjects at index date. The index date is given for each country in the table below and corresponds with the first reported Covid-19 patient in the country. All events after the index date will be excluded and subject's follow-up time will be considered only up to the index date.

Table 4 Index Dates

Country	Index Date
Argentina	02-Mar-2020
Brazil	24-Feb-2020
Croatia	24-Feb-2020
Georgia	25-Feb-2020
Israel	20-Feb-2020
Italy	29-Jan-2020
Lebanon	20-Feb-2020
Netherlands	26-Feb-2020
Poland	03-Mar-2020
Romania	25-Feb-2020
Singapore	22-Jan-2020
Spain	30-Jan-2020
Sweden ¹	NA
United Kingdom ¹	NA
Ukraine	02-Mar-2020

¹ No active subject after the index date in this country.

All inpatient hospitalisations, all urgent heart failure visits, and all deaths will be reviewed by the Clinical Endpoint Committee (CEC) to determine whether they are CV-related or not. CV hospitalisations and urgent heart failure visits will be further adjudicated as due to worsening HF, myocardial infarction, unstable angina, and other CV event.

A death with a cause classified by the adjudication committee as “unknown” will be considered as a cardiovascular death. A death with a cause classified by the adjudication committee as “undetermined” will be considered as a non-cardiovascular death. For all other cases, the final adjudicated classification will be taken into consideration for the analyses described below.

Incomplete hospitalisation dates will be imputed in the following way:

Hospitalisation start date:

1. If the start date of a hospitalisation is partially missing and the month and year or the year are equal to those of the randomisation date and the hospitalisation end date is after or equal to the randomisation date or missing, then the hospitalisation start date will be imputed as the randomisation date.
2. If the hospitalisation end date is before the randomisation date, the hospitalisation start date will be imputed as the hospitalisation end date if the month and/or year is the same.
3. If the start date is completely missing, then the start date will be imputed as the hospitalisation end date.

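### Every efficacy analysis requires that dosing was started, a step taken after allocation by staff who can see it, and none includes the outcomes of undosed subjects

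*SAP*

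**What the plan says.** SAP 3.1 makes it a condition of the FAS that "The administration of study drug was started". Protocol 12.3.1 has the same condition: "The administration of study treatment was started". The SAP adds a requirement for some post-baseline information (with an exception for later withdrawals) and removes subjects with a consent deviation. The Per-Protocol (PP) set "will consist of all subjects in the FAS who had no major protocol violations", so it inherits the dosing condition.

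SAP 4.6 states: "The analysis of the primary, secondary and other outcomes described below will be performed on the FAS". PP is the sensitivity set, and the Covid-19 and subgroup analyses also use the FAS. The SAP does define a set without the dosing condition: "The All Randomised set will be analysed based on the randomised treatment arm". Table 2 uses that set only for disposition and protocol deviations, and no efficacy table or figure in SAP 7.1 is built on it.

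Protocol 6.2 explains that the two solutions look different and that "the study treatment boxes will not be blinded". The unblinded personnel "will be responsible for handling the study treatment boxes, and preparing and administering the study treatment injections in black syringes". Under Protocol 9.2.3.13 the unblinded Investigator works out the dose from Table 1.

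On the time origin, SAP 4.2.14 says: "Time on study for efficacy purposes is calculated for each subject from randomisation date to the last known date".

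**The concern.** Leaving out subjects who were randomised but never dosed does no harm when the reason for non-dosing cannot depend on the arm. Full blinding up to the first injection would normally secure that. Here the people who carry out the first injection already know the allocation. The protocol synopsis also allows unblinded personnel to help with screening, so they may know the patient's condition as well.

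If frailer subjects in one arm went undosed more often than in the other, the dosed subjects would no longer be a randomised comparison. The PP analysis could not reveal this, because it is drawn from the same dosed subjects. The analysis exposed is the primary rate ratio, and with it the secondary endpoints tested under Hochberg's procedure.

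**Working it through.** **Step 1: are undosed subjects foreseen, and what will be shown about them?** SAP 4.4 counts subjects randomised but not treated, subjects who started treatment after the day of randomisation, and reasons for exclusion from each population. Table 14.1.1.4 and Listing 16.2.3.2 carry this on the All Randomised set. Their outcomes are another matter. The efficacy-response, adjudicated-event and hospitalisation listings (16.2.6.1 to 16.2.6.5) are on the FAS, and the death listing (16.2.7.4) is on the Safety Set, which also requires that dosing started. A reader would see how many were undosed but could not see whether their adjudicated events alter the result.

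**Step 2: the plan's own sample size.** Inputs from SAP 4.1 are a placebo rate of 0.7/year, rate ratio 0.75 (FCM rate 0.525), dispersion 1, two-sided alpha 0.05 and power 80%. Mean follow-up of 11 months (t = 0.917 years) is in the protocol synopsis. By the Zhu–Lakkis formula, with the null variance taken from the control rate:

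- V0 = 2/(0.917 × 0.7) + 2 = 5.117
- V1 = 1/(0.917 × 0.7) + 1/(0.917 × 0.525) + 2 = 5.636
- n = (1.960 × √5.117 + 0.842 × √5.636)² / (ln 0.75)² = 500 per arm

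This matches the stated 1,000. The other null-variance choices at 11 months give 1,060 or 1,070. Inflation for 9% loss is 1,000/0.91 = 1,099, against 1,100 stated. No design figure is in error.

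**Step 3: power.** With 550 per arm and 11 months, power (unpooled Wald) is 81.1%. Leaving out 1%, 2% or 3% of both arms at random gives 80.7%, 80.3% or 79.9%. Loss of numbers is not the issue.

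**Step 4: bias.** Assume that a share f of the FCM arm only is undosed and that these subjects have h times that arm's mean event rate. The expected FAS rate ratio is then:

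true ratio × (1 − f·h)/(1 − f)

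The chance of a significant result favouring FCM follows from the Wald variance (1/(0.7t) + 1)/550 + (1/(0.7t × RR) + 1)/(550(1 − f)), where RR is the expected FAS ratio. With a true ratio of 1.00:

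| f (subjects) | h | Expected FAS ratio | Chance of false result favouring FCM |
|---|---|---|---|
| any | 1 | 1.000 | 2.5% |
| 1% (about 6) | 2 | 0.98/0.99 = 0.990 | 3.2% |
| 1% (about 6) | 3 | 0.97/0.99 = 0.980 | 4.0% |
| 2% (11) | 2 | 0.96/0.98 = 0.980 | 4.0% |
| 2% (11) | 3 | 0.94/0.98 = 0.959 | 6.3% |
| 3% (about 17) | 3 | 0.91/0.97 = 0.938 | 9.5% |

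If the omission is in the placebo arm instead, the bias reverses: at f = 2%, h = 3 the ratio is 0.98/0.94 = 1.04. If the same share at the same relative risk is missing from both arms, the factors cancel.

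**Step 5: at the design effect.** Suppose 10 FCM subjects, each at 1.4 events/year, are undosed and none on placebo. The FCM arm has 550 × 0.525 = 289 events per year; removing 14 leaves 275 among 540 subjects, or 0.509. The ratio becomes 0.509/0.70 = 0.727 instead of 0.75. The log shift is 0.031, about 0.3 of the standard error of roughly 0.10.

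**Step 6: would the missing events be recorded?** Footnote 14 of the schedule of events starts endpoint checks when study treatment is first given, although adverse events are collected from consent. SAP 4.6.2 measures time to event from randomisation, yet counts subject-years at risk for the hazard rate from the start of study drug. Protocol 5.4.1 provides for continued follow-up when treatment is stopped early, but does not spell out follow-up when it was never started.

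**The case against.** The strongest reply is that the protocol leaves no choice at this step. Its synopsis has the first dose given to every randomised subject at Visit 2, eligibility is settled before randomisation (9.2.3.9), the dose follows from haemoglobin and weight, and withdrawal from study drug on safety grounds is for the Medical Monitor or Investigator (5.4.1). Allocation is central, the FAS is analysed as randomised, and the endpoint committee adjudicates blinded. The dosing condition is in the protocol itself and is not a late addition by the SAP.

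Much of this stands. A reader might infer that unblinded staff decide whether the injection goes ahead; no passage gives them that discretion. A reader might also infer that selective non-dosing would leave no trace in the outputs. That is not so, because the counts and reasons for exclusion in SAP 4.4 should show a marked imbalance. It would also go too far to say that protection against selection after allocation is lost: bias needs undosed subjects, imbalance between arms, and risk that differs from the arm average, all together.

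What the reply does not answer is that blinded adjudication protects how events are classified, not who is in the analysis set. The documents also differ on timing. The synopsis text on treatment recommends dosing on the day of randomisation, while 4.1.2, 9.2.3.12 and schedule footnote 10 require it, and the SAP provides for later starts and for none. These passages need to be reconciled.

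**Conclusion.** The point holds as an opportunity for bias, with no evidence in the documents that bias occurred. All efficacy sets are conditional on a step after allocation performed by people who can see the allocation, and no planned analysis restores the comparison of everyone randomised.

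The size cannot be fixed, because no expected number of undosed subjects is given. About 6 undosed subjects in one arm would matter little. Eleven to 17, all in the FCM arm and at three times the average risk, would move a null rate ratio to about 0.96–0.94 and raise the chance of a false finding for FCM from 2.5% to 6.3–9.5%. Those are deliberately one-sided assumptions. With equal omission, or omission unrelated to risk, there is no bias.

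A reader might go further and conclude that the All Randomised set should replace the FAS as the main analysis. The documents do not compel that. The dosed FAS is pre-specified in the protocol, and replacing it would be a trade-off.

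**What to change.** Keep the FAS as the main analysis, and make these changes:

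- In SAP Table 2 and SAP 4.6, add a pre-specified sensitivity analysis of the primary and secondary endpoints on the All Randomised set, without subjects lacking valid consent. Analyse by assigned arm, with events and time at risk counted from randomisation.
- Tabulate undosed subjects by arm, with reasons and their adjudicated events.
- Reconcile schedule footnote 14 and the at-risk time in SAP 4.6.2 with follow-up from randomisation, and state that undosed subjects are followed for endpoints. Without this the new analysis would contain little beyond the FAS.

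The cost is one extra set of runs, the work of confirming follow-up for undosed subjects, and slight dilution. For example, if 2% of the FCM arm is undosed and has the placebo rate, a ratio of 0.75 becomes 0.98 × 0.75 + 0.02 × 1.00 = 0.755. If few are undosed, the analysis simply confirms the FAS result.

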3.2. Protocol Deviations/Violations

The sponsor, or designee, will be responsible for producing the final protocol deviation/violation file (formatted as an Excel file or SAS dataset), in collaboration with Cytel and the data monitoring group as applicable; this file will include a description of each protocol deviation/violation, and will clearly identify whether or not each violation warrants exclusion from a population. This file will be finalized prior to hard database lock.

Protocol deviations will be reported in a data listing for all subjects in the All randomised.

4. STATISTICAL METHODS

4.1. Sample Size Justification

The recurrent HF hospitalisation and CV death rates in the control group were extrapolated as 0.9 events/year using the data from the EVEREST study [3] and as 0.61 events/year using the data from the ESC-HF study [4]. For this study, it is anticipated that approximately 35% of subjects will sustain either a CV death or at least one HF hospitalisation. It is also anticipated that 12% of subjects will sustain a CV death. Assuming that 50% of subjects who sustain a CV death will not undergo any prior HF hospitalisation and estimating the average number of HF hospitalisations per subject with at least one HF hospitalisation as 2, the number of events per 100 years of follow-up has been estimated as follows: 12 CV deaths + 2*(35-6) HF hospitalisations, which equates to approximately 70 events/100 years of follow-up for HF hospitalisations and CV death.

Concerning the event rate ratio, it is assumed that there will be a 30% reduction in HF hospitalisations for subjects allocated to FCM and that CV death rates will be similar between the FCM and placebo groups. It is therefore assumed that the rate ratio between FCM and placebo for the composite of recurrent HF hospitalisations and CV deaths will be approximately 25%.

The dispersion factor used in negative binomial regression is a measure of the mean-variance. There are currently insufficient data to estimate the negative binomial dispersion. For this sample size calculation, a dispersion factor (K) of 1 was assumed.

The sample size calculation was done in the software NCSS PASS-14 [5], using the sample size formula proposed by Zhu and Lakkis 2014 [6] to compare two negative binomial rates.

Assuming a rate of recurrent HF hospitalisation or CV death of 0.7 events/year in the placebo group, a total of 1,000 subjects (500 per study drug group) would be required to demonstrate a statistically significant rate ratio of 0.75 (i.e., 25% reduction of recurrent hospitalisations or deaths between the FCM and placebo groups) with a power of 80% and a 2-sided alpha of 0.05. Taking into account an expected 9% loss to follow-up, a sample size of 1,100 subjects (550 per treatment group) is planned.

4.2. General Statistical Methods and Data Handling

4.2.1. General Methods

Tabulations will be produced for appropriate demographic, baseline, efficacy, and safety parameters. For categorical variables, summary tabulations of the number and percentage of subjects within each category of the parameter will be presented (with a category for missing data if appropriate). For continuous variables, the mean, median, standard deviation (SD), first and third quartiles (Q1 and Q3), and minimum and maximum values will be presented. The level of significance to be used for tests will be 0.05, two-sided.

Listings will be sorted by subject ID unless specified otherwise.

Label of the group treated with Intra Venous Ferric CarboxyMaltose will be “FCM”, placebo group will be labelled as “Placebo”.

All outputs will be incorporated into Word files, sorted and labelled according to the International Council for Harmonisation (ICH) recommendations, and formatted to the appropriate page size(s).

4.2.2. Computing Environment

All descriptive statistical analyses will be performed using SAS statistical software (Version 9.4 or later), unless otherwise noted. Medical history and adverse events will be coded using MedDRA. Medications will be coded using the World Health Organization (WHO) Drug dictionary. Versions of dictionaries will be indicated in the footnote of the relevant tables and listings.

4.2.3. Methods of Pooling Data

AFFIRM-AHF database will be pooled with FAIR-HF2 (ClinicalTrials.gov Identifier: NCT03036462) and FAIR-HFpEF (ClinicalTrials.gov Identifier: NCT03074591) studies and integrated analyses will be performed:

- Integrated analysis 1: AFFIRM-HF and FAIR-HF2 studies
- Integrated analysis 2: AFFIRM-HF, FAIR-HF2 and FAIR-HFpEF studies

Specific integrated SAPs will be written for this purpose.

4.2.4. Adjustments for Covariates

Adjustments will be made for the following baseline covariates as measured at time of randomisation: sex, age, HF aetiology (ischaemic/non-ischaemic/unknown), HF duration category (newly diagnosed at Index hospitalisation/known documented HF prior to Index hospitalisation) and country. If there are too few subjects in some countries, country can be replaced for the adjustments by region as described in section 4.5.1.

4.2.5. Multiple Comparisons/Multiplicity

There will be no adjustment for multiplicity.

4.2.6. Subpopulations

Some analyses will be performed on the following subgroups:

- Hb level at baseline (< 12, ≥ 12 g/dL).
- Ferritin level at baseline by tertiles.
- Ferritin level at baseline (< 100 ng/mL, ≥ 100 ng/mL).
- TSAT category at baseline by tertiles.
- TSAT category at baseline (< 20%, ≥ 20%).
- Sex.
- Age by tertiles.
- Renal function at baseline defined as No CKD, CKD stages I and II, and CKD stages III, IV, or V at baseline medical history.
- Estimated glomerular filtration rate (eGFR) value at baseline by tertiles. The eGFR value at baseline will be calculated using the CKD-EPI formula and the baseline creatinine value.
- Ischaemic Aetiology of HF (ischaemic, non-ischaemic).
- NYHA at baseline (NYHA II, NYHA III, if applicable, i.e. if there are at least 10% of subjects by NYHA class and treatment group. NYHA I and IV not included).
- NT-pro BNP (pg/mL) or BNP (pg/mL) at baseline assigned to First tertile, Second tertile or Third tertile. Tertiles of NT-proBNP and BNP at baseline in FAS regardless of treatment group will be computed (for each parameter separately) and subjects will be assigned to these groups. In case subject has both values collected at baseline, NT-proBNP will be used and subject will be assigned according to computed NT-proBNP tertiles.
- Left ventricular ejection fraction (%) at baseline Left ventricular ejection fraction (LVEF) < 25%, ≥ 25% until < 40%, and ≥ 40% until < 50%
- Diagnosis of Heart Failure (newly diagnosed at index hospitalisation, known documented HF prior index hospitalisation).
- Subjects hospitalised for an episode of Acute Heart Failure in the previous 12 months prior Index Hospitalisation (yes, no).
- Creatinine at baseline by tertiles.

For subgroups defined by tertiles, tertiles will be computed on the FAS regardless of treatment group.

Additionally, following subgroups will be investigated for exploratory purposes:

- Geographical region (Latin America [Argentina, Brazil], Asia [Israel, Lebanon, Singapore], South and Eastern Europe [Italy, Croatia, Georgia, Romania, Ukraine], Central and Western Europe [Netherlands, Poland, United Kingdom, Spain, Sweden])
- Subjects with ARNI (yes, no)
- Subjects with ACE or ARB or ARNI, at least one of these groups (yes, no)
- Subjects with beta-blockers (yes, no)
- Subjects with Aldosterone Antagonists (yes, no)
- Subjects with triple therapy (defined as ACE or ARB or ARNI (any of these groups) and beta blockers and Aldosterone Antagonists) versus subject without the triple therapy

See section 4.8.8 and Appendix IV for definition of the medication of special interest categories. Medications will be considered for these subgroups if they were taken by the subject at the time of randomisation. Analyses for these six subgroups will not be part of the main set of outputs.

